5.4.1 Growth data

SDS will be calculated using the current formulae provided by the WHO as follows:

- $\frac{\left(\frac{X}{M}\right)^{L}-1}{2}$
- 1. Calculate $z_{ind} = LS$
- 2. If $|z_{ind}| \le 3$, $SDS = z_{ind}$

If $z_{ind} > 3$, SDS = 3 + (X - SD3pos) / SD23pos

If $z_{ind} < -3$, SDS = -3 + (X - SD3neg) / SD23neg

where:

- *X* is height in centimeters or BMI in kilograms/ m^2 ,
- *L*, *M* and *S* are height or BMI-, sex- and age-specific reference values from the WHO Growth Charts.
- SD3*pos* is the cutoff 3SD calculated by the LMS method: SD3*pos* = M * $(1 + LS*3)^{1/L}$

- SD3*neg* is the cutoff -3SD calculated by the LMS method: SD3*neg* = M * $(1 + LS^*(-3))^{1/L}$
- SD23*pos* is the difference between the cutoffs 3SD and 2SD: SD23*pos* = M * $(1 + LS*3)^{1/L}$ - M * $(1 + LS*2)^{1/L}$
- SD23*neg* is the difference between the cutoffs -2SD and -3SD: SD23*neg* = M * $(1 + LS^*(-2))^{1/L}$ - M * $(1 + LS^*(-3))^{1/L}$

Height-for-age and BMI-for-age L, M and S reference values for males and females are available under [http://www.who.int/childgrowth/standards/en/] (for patients aged between 0 to 5 years old) and [http://www.who.int/growthref/en/] (for patients aged between 5 to 19 years old). These correspond to the latest available international references available at this time and described in the 2007 Bulletin of the WHO [Mercedes de Onis et al 2007]. Note: use age in months at time of assessment "(visit date – date of birth) / 30.4375" rounded down to the nearest whole month for corresponding values of L, M and S. SDS is actually a Z score that measures the distance from the population mean in units of standard deviations. That is, SDS < 0 refers to values lower than the population mean, and for example SDS \leq -1.645 refers to values in the lowest 5%.

The SDS score can be converted to a percentile assuming a standard normal distribution [mean=0, standard deviation =1]. Percentiles will also be grouped into the following categories: $<1^{st}$ percentile, ≥ 1 to <3, ≥ 3 to <5, ≥ 5 to <15, ≥ 15 to <25, ≥ 25 to <50, ≥ 50 to <75, ≥ 75 to <85, ≥ 85 to <95, ≥ 95 to <97, ≥ 97 to <99, ≥ 99 .

Note that BMI is reported instead of weight as no reference data are provided by the WHO for age beyond 10.

Height velocity is defined as follows:

Height velocity (cm/6-months) = (height in time window k – height in time window k-1) ÷ ([assessment date in time window k – assessment date in time window k-1] ÷ [365.25/2]), and similarly for weight velocity.

Velocity SDS is calculated as (velocity – mean) / standard deviation, where mean and standard deviation are obtained as the height-, weight-, sex- and age-specific values [Baumgartner et al 1986], where the age category immediately above the patient's exact age (at the assessment date in time window k) should be used. Velocity SDS will only be calculated for time window k if data also exists for time window k-1, since calculating across multiple units of 6 months requires more than one reference value to be taken into account.

Table 5-3 summarizes the time windows for growth data, where windows are centered at every 6 months after start of study treatment. Although height and weight are collected more frequently than every 6 months (post-enrollment), this choice of time window length was made to reflect the degree of accuracy in the reference values (every 6 months) that will be used in the calculation of summary variables of growth.

In case of multiple assessments falling into the time window interval, the closest to the target date will be considered. For example, if there are three assessments falling under the time window of Day 85 to 252, then the closest one to target day of 168 will be considered. If two assessments are equidistant from target date, the average will be considered of those respective assessments.

Table 5-4	Time windows for growth data (height SDS, height velocity, weight
	velocity, BMI SDS)

Planned assessment	Time window	
Baseline	Days ≤1	
Month 6 (Day 168)	Days 85 – 252	
Month 12 (Day 336)	Days 253 – 420	
Month 18 (Day 504)	Days 421 – 588	
Month xx (Day xx * 28)	Days ((xx – 3) * 28 + 1) – Day ((xx + 3) * 28)	
End of Treatment (EoT)	Earliest data available on or after EoT date up to and including 30 days after EoT	
Day 1 = date of first intake of study drug		
xx = Every 6 months		

5.4.2 Bone Age

Bone age SDS will be calculated as (bone age – chronological age) / standard deviation) where the chronological age is the age in months at the time of the X-ray evaluation and standard deviation is the sex- and age-specific standard deviation, as defined in the table below:

Table 5-5	Variability in Bone Age		
Chronologic Age in Months	Boys Standard Deviation	Girls Standard Deviation	
12	2.1	2.7	
18	2.7	3.4	
24	4	4	
30	5.4	4.8	
36	6	5.6	
42	6.6	5.5	
48	7	7.2	
54	7.8	8	
60	8.4	8.6	
66	9.1	8.9	
72	9.3	9	
84	10.1	8.3	
96	10.8	8.8	
108	11	9.3	
120	11.4	10.8	
132	10.5	12.3	
144	10.4	14	
156	11.1	14.6	
168	12	12.6	
180	14	11.2	
192	15	15	
204	15.4	15.4	

Novartis	Confidential	Page 63
SAP Final CSR LGG		CDRB436G2201

If the chronologic age falls between two values in the table above, the closest age should be used. If the chronologic age falls exactly in the middle between 2 values in the table above, then the age above the chronologic age should be used.

Table 5-6Time windows for bone data

Planned assessment	Time window	
Baseline	Days ≤ 1	
Month 6 (Day 168)	Days 85 – 252	
Month 12 (Day 336)	Days 253 – 420	
Month 18 (Day 504)	Days 421 – 588	
Month xx (Day xx * 28)	Days ((xx – 3) * 28 + 1) – Day ((xx + 3) * 28)	
End of Treatment (EoT)	Earliest data available on or after EoT date up to and including 30 days after EoT	
Day 1 = date of first intake of study drug		
xx = Every 12 months		

5.5 Statistical models

5.5.1 Primary analysis

Responses will be summarized in terms of percentage rates with 95% CIs. An exact binomial CI (implemented using SAS procedure FREQ with EXACT statement for one-way tables) will be calculated [Clopper CJ and Pearson ES. (1934) The use of confidence or fiducial limits illustrated in the case of the binomial. Biometrical, 26, 404-413].

SAS procedure FREQ will be used to estimate the proportion of responders (binary outcome = 1 or "Yes"), along with the associated 95% (= $100 \times (1 - two-sided alpha level$)) two-sided Pearson-Clopper CI and exact one-sided p-value for the hypothesis test of the *null proportion* (0.10).

When there are no responders, SAS does not produce a CI by default. To obtain a CI in this situation, PROC FREQ is used by changing level = "No". From the results of this modified procedure, the values in percent of the LCL and UCL of a 0% response rate are calculated as follows:

$$LCL_{LEVEL="Yes"} (\%) = 100\% - UCL_{LEVEL="No"} (\%)$$

 $UCL_{LEVEL="Yes"} (\%) = 100\% - LCL_{LEVEL="No"} (\%)$

Multiplicity adjustment

Not applicable.

5.5.2 Key secondary analysis

Not applicable.

5.5.3 Secondary efficacy analysis

Kaplan-Meier estimates

Novartis	
SAP Final CSR LGG	

To analyze time to event endpoints (TTR, DOR, PFS and OS). An estimate of the survival function will be constructed using Kaplan-Meier (product-limit) method as implemented in PROC LIFETEST with METHOD=KM option. The PROC LIFETEST statement will use the option CONFTYPE=LOGLOG. The TIME statement will include a variable with survival times and a (right) censoring variable with a value of 1, representing censoring. Kaplan-Meier survival and failure function estimates from this procedure will be used to construct the Kaplan-Meier figures.

Median survival will be obtained along with 95% CI calculated from PROC LIFETEST output using the method of [Brookmeyer R and Crowley J. (1982)]. Kaplan-Meier estimates of the survival function with 95% CI at specific time points will be summarized. The standard error of the Kaplan-Meier estimate will be calculated using Greenwood's formula [Collet D (1994).].

Hazard ratio

Hazard ratios will be estimated by fitting the Cox proportional hazards model using SAS procedure PHREG (with TIES=EXACT option in the MODEL statement).

An unadjusted Cox model will be used, i.e. the MODEL statement will include the treatment group variable as the only covariate.

Hazard ratio with two-sided 95% CI will be based on Wald test.

Treatment of ties

The STRATA statement in LIFETEST procedure will be used to analyze time to event data with ties. The PHREG procedure in SAS with option TIES=EXACT will be used to fit the Cox proportional hazards model.

5.5.4 Implementation of RANO guidelines (protocol Appendix 3)

As described in the protocol, the ORR will be evaluated by RANO criteria for solid tumors. This section provides some details on how to derive these endpoints by RANO and further details are included in the protocol Appendix 3.

The RANO criteria for assessment of LGG differs from that for HGG primarily in that LGG assessments utilize T2/FLAIR imaging rather than contrast enhancement as these tumors rarely enhance while HGG assessments utilize Gadolinium enhanced imaging. LGG cohorts will be assessed per LGG modification of RANO criteria with the exception that minor response will not be evaluated as per protocol.

The major differences between RECIST 1.1 and RANO include:

- The measurability criteria for target lesion by RANO is based on two dimensions i.e two perpendicular diameters are measured for each target lesion;
- Corticosteroids use and clinical status are also considered for determining overall response;
- T2/FLAIR will be used for both measurable and non-measurable disease

Novartis	Confidential	Page 65
SAP Final CSR LGG		CDRB436G2201

Overall Lesion Response Collected on RANO eCRF page

In this study, Independent reviewer reported overall response and Investigator reported overall lesion response will be used for primary and secondary endpoints.

For investigator, the overall response by RANO will be derived based on the collected overall lesion response on eCRF page "RANO Overall Lesion Response" (ZR domain, ZRCAT = "RESPONSE ASSESSMENT IN NEURO-ONCOLOGY", and ZRSCAT = "OVERALL LESION RESPONSE").

For independent reviewer, the overall response by RANO will be derived based on the collected overall lesion response on eCRF page "RANO Overall Lesion Response" (ZR domain, ZRCAT = "RESPONSE ASSESSMENT IN NEURO-ONCOLOGY", and ZRSCAT = "OVERALL RESPONSE").

There will be two evaluations at a given assessment for independent reviewer i.e. primary RANO radiologic review without clinical data (read 1 – ZREVAL = "PRIMARY REVIEW") and a secondary RANO review with clinical data (read 2 – ZREVAL = "SECONDARY REVIEW"). Secondary RANO review (read 2) with clinical data will be used for the primary endpoint of BOR per independent review. Primary review (read 1) will be used in supportive analyses based on radiographic review only, without clinical data.

Calculation of Overall Lesion Response by RANO

Overall lesion responses by RANO are also calculated from the following components:

- 1. Target lesion measurements;
- 2. Non-target lesion response;
- 3. New lesion present (Yes/No);
- 4. Corticosteroids use;
- 5. Clinical status.

All these components are collected on the following eCRF pages:

- 1. RANO target lesion Measurable enhancing lesion (T1) (ZI domain, ZICAT = "MODIFIED RANO CRITERIA FOR BRAIN METASTASES", ZISCAT = "MEASURABLE T2/FLAIR");
- RANO non-target lesion Non-measurable enhancing lesion (T1) (ZI domain, ZICAT = "MODIFIED RANO CRITERIA FOR BRAIN METASTASES", ZISCAT = "NON-MEASURABLE T2/FLAIR");
- RANO New Lesion (ZI domain, ZICAT = "MODIFIED RANO CRITERIA FOR BRAIN METASTASES", ZISCAT = "NEW");
- 4. Corticosteroids use and clinical status are collected on the Modified RANO Assessment (ZR domain, ZRCAT = "MODIFIED RANO CRITERIA FOR BRAIN METASTASES", ZISCAT = "RESPONSE ASSESSMENT").

All the above components are collected on the same eCRF pages for independent reviewer with the exception of ZICAT = " RESPONSE ASSESSMENT IN NEURO-ONCOLOGY".

Novartis	Confidential	Page 66
SAP Final CSR LGG		CDRB436G2201

Each target lesion by RANO criteria has two perpendicular diameters collected. In order to calculate the target lesion response, the product of the two perpendicular diameters is calculated for each target lesion. Then the sum of the products of diameters of all target lesions is compared to the baseline or nadir to determine the target lesion response.

The non-target lesion response is collected on the field of "Non-target lesion present" in the Modified RANO Assessment page, and is evaluated based on both non-target lesion eCRF pages as shown above. However, no derivation will be performed from individual non-target lesion status to non-target lesion response.

The RANO response/progression criteria are summarized in .

	CR	PR	SD	PD
T2/FLAIR	None	≥50% decrease from baseline	<50% decrease from baseline but <25% increase from nadir	≥25% increase from nadir*
New Lesion	None	None	None	Present*
Corticosteroids	None	Stable or decreased	Stable or decreased	NA**
Clinical Status	Stable or improved	Stable or improved	Stable or improved	Worsened*
Requirement for Response	All	All	All	Any*
CR=complete response; PR=partial response; SD=stable disease; PD=progressive disease				

 Table 5-7
 Summary of the RANO response criteria

*: Progression occurs when this criterion is met

**: Not Applicable (NA): Increase in corticosteroids alone will not be taken into account in determining progression in the absence of persistent clinical deterioration Note: The minor response category will not be utilized in this study.

Two fields in the Modified RANO Assessment page will not be used for any data analysis in the study: "New enhancement outside radiation field?", "Tumor present in histopathology".

5.5.5 Mixed Model for Height SDS

A mixed model will be used to estimate differences of change from baseline in height SDS between treatment groups. A mixed model with height SDS as the response variable and time, gender, and treatment as explanatory variables will be fit using PROC MIXED.

Two copies of visit number in integer (AVISITN) will be used to proxy the time of measurements. One copy of the time measure AVISITN is created and named TIME to specify the model with a continuous time measure (used for fixed effects) and the other named MONTH to specify the model with a categorical time measure (used for random effects).

In this model, as a first approach, a mixed model with an unstructured variance-covariance matrix will be used to model the correlation within patients. The structure of the correlation matrix and the use of random intercept will be further investigated if the first approach fails to converge. Therefore, we proposed the following sequence of model fits:

- 1. Step 1: Repeated measures with an unstructured variance-covariance matrix.
- 2. If it fails to converge, try the random intercept model with a AR(1) variance-covariance matrix for the repeated measures.

Below are the SAS codes for reference.

FIT 1

PROC MIXED DATA=SCC METHOD=REML;

CLASS TRT01AN USUBJID MONTH SEXN;

MODEL AVAL=TRT01AN TIME TRT01AN*TIME SEXN / SOLUTION DDFM=KENWARDROGER;

REPEATED MONTH / SUBJECT=USUBJID TYPE=UN;

ESTIMATE 'slope TRT D+T' TIME 1 TIME*TRT01AN 1 0;

ESTIMATE 'slope TRT C+V' TIME 1 TIME*TRT01AN 0 1;

ESTIMATE 'slope (D+T) - (C+V)' TIME*TRT01AN 1 -1;

LSMEANS TRT01AN / PDIFF CL;

RUN;

FIT 2

PROC MIXED DATA=SCC METHOD=REML;

CLASS TRT01AN USUBJID MONTH SEXN;

MODEL AVAL=TRT01AN TIME TRT01AN*TIME SEXN / SOLUTION DDFM=KENWARDROGER;

RANDOM INTERCEPT / SUBJECT=USUBJID;

REPEATED MONTH / SUBJECT=USUBJID TYPE=AR(1);

ESTIMATE 'slope TRT D+T' TIME 1 TIME*TRT01AN 1 0;

ESTIMATE 'slope TRT C+V' TIME 1 TIME*TRT01AN 0 1;

ESTIMATE 'slope (D+T) - (C+V)' TIME*TRT01AN 1 -1;

LSMEANS TRT01AN / PDIFF CL; RUN;

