2.8.4.7 Growth and development (Height and Weight)

Growth data consist of height, BMI, height SDS, BMI SDS, height velocity SDS, weight velocity SDS, height velocity and weight velocity.

Height and weight will be summarized at 6-month intervals during the on-treatment period, using the SDS, velocity and velocity SDS. The relevant height and weight values for each 6-month period are defined using time windows, as defined in Table 5-4. The z-scores will allow identification of potential outliers.

The formula used to calculate the SDS and height and weight velocities are provided in the Appendix 5.4.2.

Note that BMI SDS are reported instead of weight SDS as no reference data for weight are provided by the WHO for age beyond 10.

Height and BMI SDS and height and weight velocity SDS will be summarized using descriptive statistics (mean, standard deviation, median, Q1, Q3, minimum, maximum) for each time window (at Baseline and thereafter allowing informal comparison of growth data), as well as by presenting number of patients with SDS values lower/higher than $5^{th}/95^{th}$ percentiles respectively.

Box plots will be plotted for each time window. A shift table to compare baseline SDS to the worst on-treatment SDS categorized as Low (SDS <- 1.645), High (SDS > 1.645) or Normal (- $1.645 \le SDS \le 1.645$) will be produced for height and BMI SDS. Another shift table to compare the baseline height SDS to the last available on-treatment height SDS categorized according to the main percentile lines (>95th, 95th to 90th, 90th to 75th, 75th to 50th, 50th to 25th, 25th to 10th, 10th to 5th and \le 5th percentile) will be produced.

In addition, a mixed model will be used to estimate differences of change from baseline in height SDS between treatment groups. A mixed model with height SDS as the response variable and time, gender, and treatment as explanatory variables will be fit using PROC MIXED. See Appendix 5.4.5 for model specifications and further details.

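### The final LGG height-SDS model uses visit number as time without placing the end-of-treatment record, and its LSMEANS line compares level rather than change from baseline

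*SAP*

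**What the plan says.** All references are to the final-analysis LGG SAP unless stated.

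- **Aim.** Section 2.8.4.7 says that "a mixed model will be used to estimate differences of change from baseline in height SDS between treatment groups", and section 5.5.5 repeats it.
- **Time variable.** Section 5.5.5: "Two copies of visit number in integer (AVISITN) will be used to proxy the time of measurements". One copy is "named TIME to specify the model with a continuous time measure (used for fixed effects"; the other, MONTH, is categorical and indexes the repeated measures.
- **Mean model, both fits.** "MODEL AVAL=TRT01AN TIME TRT01AN*TIME SEXN / SOLUTION DDFM=KENWARDROGER". The response is the SDS level, and there is no baseline SDS term.
- **Contrasts.** The code gives a slope per arm, the slope difference "ESTIMATE 'slope (D+T) - (C+V)' TIME*TRT01AN 1 -1", and "LSMEANS TRT01AN / PDIFF CL".
- **Growth windows.** Table 5-4 (section 5.4.1) centres windows on days 168, 336, 504 and so on. It also has an EoT row, defined as "Earliest data available on or after EoT date up to and including 30 days after EoT". The growth table in LGG SAP Amendment 1 (section 5.3.1, Table 5-3) has no EoT row, while the model in its section 5.4.5 is the same.
- **Treatment length.** Section 1.1 gives the chemotherapy arm a fixed course and lets the targeted-therapy arm continue until progression, loss of benefit or another stopping reason.

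**The concern.** A slope on visit number is a slope on time only if the number is proportional to elapsed time. That holds approximately for the equally spaced month windows. It cannot hold for a single EoT number, because EoT has no fixed day and falls at different times in different patients, and earlier in one arm than in the other. The resulting timing error would then differ by arm, which is how a between-arm slope difference can arise without any difference in growth. The same error would flatten both fitted slopes and so hide a real decline. In a paediatric safety analysis both directions matter.

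The LSMEANS line raises a separate question. The stated aim is change from baseline, but LSMEANS for treatment with no baseline term compares mean SDS level at the average value of TIME.

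**Working it through.** The SAP gives no effect size or power for this model, so there is no figure of its own to reproduce.

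**1. Windows.** Month xx runs from day (xx-3)×28+1 to (xx+3)×28. For 6, 12 and 18 this gives 85-252, 253-420 and 421-588, matching Table 5-4. Each window is 252-85+1 = 168 days wide, so even a scheduled record can sit well away from its nominal time.

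**2. EoT timing by arm (section 1.1).** Chemotherapy: 10+2 weeks of induction plus 8×6 weeks of maintenance = 60 weeks at most. Targeted therapy: no fixed end.

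**3. Simulation with equal true slopes.** From the SAP: about 102 patients at 2:1, so 68 and 34; fixed effects treatment, TIME, treatment×TIME and sex. Assumed: between-patient SD 1.0; residual SD 0.15; EoT at 0.6-1.15 years (chemotherapy) and 1.5-3.5 years (targeted); visit number equal to month number. The fit was random-intercept REML, a simplified form of the SAP's second fit without AR(1), with a 1.96 cut-off and 200 runs per cell. The table shows how often the slope-difference test rejected (nominal 5%).

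| EoT handling | slope 0 | -0.1/year | -0.2/year |
|---|---|---|---|
| excluded | 4% | 7% | 6% |
| true elapsed time | 2% | 7% | 5% |
| last window + 6 | 4% | 7% | 19% |
| coded 66 | 10% | 100% | 100% |
| coded 99 | 7% | 97% | 100% |
| coded 999 | 3% | 65% | 98% |

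With EoT excluded or truly timed, the mean slope difference was within 0.006 SDS/year of zero.

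**4. Hand check, code 66, slope -0.1.** Code 66 stands for 66×28/365.25 = 5.06 years. Mean EoT is (0.6+1.15)/2 = 0.875 years (chemotherapy) and (1.5+3.5)/2 = 2.5 years (targeted), so the true changes at EoT are -0.0875 and -0.25 SDS. Spread over 5.06 years they give -0.017 and -0.049 per year, a difference of about -0.03. The simulation gave -0.013 and -0.050, a difference of -0.037. With code 99 it gave -0.008 and -0.029. All of these should be -0.1 in both arms.

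**5. LSMEANS.** With EoT excluded or truly timed, the level difference averaged about 0 and rejected in 3-6% of runs. With EoT coded 66, 99 or 999 and a trend, it averaged about -0.09 to -0.19 and rejected in 6-18%. Chance baseline imbalance at an assumed SD of 1 has SE √(1/68+1/34) = 0.21 SDS, or ±1.96×0.21 = ±0.41, and an unadjusted level difference carries it in full.

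**The case against.** The strongest reply is that the mechanism is conditional. Nothing in the SAP assigns EoT a visit number or says that EoT records enter the modelling dataset, and section 5.5.5 does not mention EoT. The name MONTH and the six-monthly summaries in section 2.8.4.7 suggest month-numbered windows. For patient-reported outcomes, section 2.1.1 places EoT data in the corresponding time window, so an out-of-sequence code cannot be presumed. All of this stands. It does not settle the matter, because the patient-reported-outcome rule is not extended to growth and the final SAP added the EoT row without adapting the model.

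Other points also stand:

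- The simulation resembles a simplified second fit. The first planned fit, with unstructured covariance, was not simulated.
- With no common trend, rejection was 2-10% under every coding.
- The slope difference is already coded and does address change.
- A reader might infer that LSMEANS produces a false arm effect. Under randomisation, with EoT excluded or correctly timed, it does not: the 0.21 is ordinary sampling error that its own standard error covers.
- A reader might also suspect the 28-day month. It only rescales both slopes, by 28/30.4375 = 0.92, and does not distort the comparison.
- Section 2.7.2 rules out inferential analyses for secondary objectives, which include safety. The growth summaries, box plots and shift tables in section 2.8.4.7 do not use TIME.

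**Conclusion.** The point holds as a weakness in the specification with a better method readily available. Visit number is a coarser time variable than the assessment dates, and Table 5-4 now contains a record that visit number cannot place. A spurious slope difference needs three things together: EoT records in the model, a number out of time order, and a common trend in height SDS. Under those conditions and the assumed durations and SDs, null rejection at -0.1 SDS/year was 65-100%, against 7% otherwise. In-order coding as the next window is milder but not harmless, at 19% for -0.2 SDS/year.

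A reader might infer that the planned analysis will show a false growth effect. The documents do not support that, since the first two conditions are left open and the third is unknown.

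Separately, the LSMEANS output answers a question about level and should not be reported as change from baseline. Overall this is a free improvement of minor to moderate severity, because the final LGG analysis is descriptive.

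**What to change.** In section 5.5.5:

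1. Set TIME = (assessment date - start of study treatment)/365.25 for every record. This also removes the timing error inside the 168-day windows. Section 5.4.1 already uses assessment dates for height velocity.
2. Keep MONTH only as the repeated-effect index, and map the EoT record to its month window or exclude it. If it is mapped, apply the existing closest-to-target rule in section 5.4.1 so that each patient has one record per MONTH level.
3. State that the slope difference already coded is the result for the change-from-baseline objective.
4. Drop the LSMEANS/PDIFF line, or replace it with a contrast in change from baseline at common visits with baseline SDS as a covariate. The patient-reported-outcome model in section 2.10 already adjusts for baseline.

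The cost is a few lines of SAS and a short text change. The dates are already held and no new data are needed.
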